Patient and patient surrogates will be approached about enrolling their family member into this study. When appropriate, both the surrogate and patient will be approached together to explain the study and obtain consent. Patient's ability to make an informed decision will be assessed by multiple methods including speaking with the nurse and physician caring for the patient as well as the patient's family (legally authorized representative). An assessment for delirium will be performed to determine if the patient is delirious (CAM-ICU). Informed consent will be obtained from the surrogate when the patient is unable to provide consent and from the patient when they are deemed able to provide consent. If the patient is conscious and communicating with study staff, but unable to provide formal consent, we will ask them for assent regarding study activities. Specifically, if the patient refuses study related blood draws including before and during phlebotomy attempts, we will not continue. Blood draw attempts will be limited to two (2). Furthermore, if during the course of the study, the subject should become sufficiently cognitively capable of understanding the nature of his/her participation in the research study and is capable of communicating, consent will be obtained from the subject. If the subject does not give consent to continue study activities, study participation will stop. When the surrogate is not physically present at the hospital (i.e., COVID-19 visitor restrictions or other reasons). They will be contacted via phone. We will request permission to discuss the study and, if permitted, provide a summary of study activities. If the surrogate is interested, we will email consent paperwork and the study information sheet to the surrogate. We will then review the consent paperwork and answer any questions. If the surrogate gives consent, we will have them sign the consent paperwork and return it to us via our lab email ([contact]). Study activities will start only after signed consent is obtained. Alternatively, we may use the EPIC-based consent system to transmit and receive the signed consent. Use of the EPIC-based consent system will not alter communication over the phone with the surrogate.

Evaluation of Subject(s) Capacity to Provide Informed Consent/Assent: Subject ability to consent will be assessed via standard delirium assessment (CAM-ICU) and agitation assessment (RASS). Barriers to communication between the patient and study staff (visual, hearing impairment) will also be assessed. In the case of delirium, agitation, or communication difficulty, formal surrogate consent will be obtained along with informal agreement from the patient (assent) when possible.

PROTECTION OF PARTICIPANT PRIVACY

All PHI and subject data will be collected and maintained electronically. Data management procedures will ensure accurate and efficient data collection and analysis; confidentiality and real-time, on-demand study monitoring reports. All data will be maintained in accordance with HIPAA guidelines for participant confidentiality and privacy. All data will reside on secure, HIPAA-compliant database and file-sharing resources managed by the Data Management and Informatics Core (DMIC) of the POA and by Yale ITS. Access to data resources will be strictly limited to research staff and investigators, and all such resources will reside on a local network not accessible outside the secure Yale environment. All study data will be managed using REDCap, a secure, web-based data collection and workflow management system developed at Vanderbilt University and supported by the national Clinical and Translational Science Award (CTSA) program. REDCap's authentication, security and auditing features comply with the FDA Title 21 CFR Part 11 guidelines for Electronic Records and Electronic Signatures. Yale's implementation of REDCap is managed jointly by POA/DMIC and by Yale ITS, and has been certified by Yale's Information Compliance Office as meeting HIPAA privacy and security guidelines.

METHODS FOR SECURITY OF STORAGE AND SHARING MATERIALS

Outcome data will be shared, along with associated demographic and clinical data including age, gender, race/ethnicity, evaluation of functional status, and medical conditions. To enable the widest dissemination of data, while also protecting the privacy of study participants and the utility of the data, we will de-identify and mask potentially sensitive data elements, consistent with HIPAA considerations and in full compliance with the NIH public data sharing policy (for further details, see http://grants.nih.gov/grants/policy/data_sharing). Data sets will be subjected to cleaning and quality control measures. Following these procedures, for experiment types such as RNAseq and metabolomics, the data will be deposited in relevant public databases (e.g., the Gene Expression Omnibus (GEO), the Sequence Read Archive (SRA), the database of Genotypes and Phenotypes (dbGaP) and the Metabolomics Workbench) as required by the NIH and by journals. We will comply with NIH expectations for data release specified in the Supplemental Information to the GDS Policy (as outlined at http://gds.nih.gov/pdf/supplemental_info_GDS_Policy.pdf). Data will be shared once the data have been cleaned and quality control procedures are completed. Generally speaking, these procedures should be completed by 3-6 months after data generation. As per the GDS policy, after submission begins, data will be held in an exchange area accessible only to the submitting investigators and collaborators for a six-month period, after which the data will be available for research access without restrictions on publication. Final analyses relating these data to specific biologic outcomes will be released with publication. The consent form provides consent for the data to be used for future research purposes and to be shared broadly through unrestricted-access databases.

STUDY RISKS

There is minimal risk to subjects. There are no changes to usual MICU care during the observational portion of this study (Aim 1 and 2). For all enrolled patients, there is minimal risk of breach of confidentiality. There is a risk of minor skin irritation caused by Actiwatch Spectrum device application. Urine collection will be from catheterized urine that would otherwise be discarded; patients will not be catheterized to collect urine for the study. Patients who are enrolled in Aim 3 regarding the feasibility and effect size of daytime bright light will also be exposed to a bright light device set to deliver 10,000 lux at the surface of the lamp; at the planned distance of 36 inches this will degrade to <1250 lux. Direct bright light exposure (i.e. during treatment for outpatient circadian disorders) has minor and reversible side effects of eye strain, visual disturbance, and headache. If symptoms develop, light therapy will be discontinued, and the side effect will be tracked as a metric of feasibility. Also, hypomania and mania in patients with a history of bipolar disease have also been reported as uncommon but serious side effects of overexposure to light therapy. Patients with a history of bipolar disease will be excluded from the study.

MINIMIZING RISKS

The above-mentioned risks will be minimized in the following manner: Risks regarding patient confidentiality are minimized via data management strategies which isolate all personal identifying data elements. Only users having project-specific access rights can view or modify personal identifying information or print reports that include patient names or other identifying information. This study will have no paper records other than the consent forms which are stored within a locked file cabinet in the PI's office. The office is locked when not occupied. All electronic data will be maintained on a secure, firewalled server.

Skin irritation from the Actiwatch Spectrum or iButton device can be mitigated by movement of device to a contralateral site. If skin irritation is severe, the Actiwatch Spectrum or iButton will be removed, and study participation will be discontinued. If symptoms (eye strain, visual disturbance or headache) develop, light therapy will be discontinued, and the side effect will be tracked as a metric of feasibility. In addition, hypomania and mania in patients with a history of bipolar disease have also been reported as uncommon but serious side effects of overexposure to light therapy. Patients with a history of bipolar disease will be excluded from the study.

DATA AND SAFETY MONITORING PLAN

[figure not shown]
Data and Safety Monitoring for Clinical Trials: This protocol presents minimal risks to the subjects and Unanticipated Problems Involving Risks to Subjects or Others (UPIRSOs), including adverse events, are not anticipated. In the unlikely event that such events occur, the following Data and Safety Monitoring for Clinical Trials Plan will be followed.

Main Study DSMP

A **medical monitor** will oversee the proposed research project. **[name]**, Yale-New Haven Hospital MICU attending and board certified in critical care medicine, has agreed to serve as project medical monitor. She has no conflicts of interest with this role. [name] will conduct interim monitoring of accumulated data from research activities to assure the continuing safety of participants and integrity of the accumulating data. The medical monitor is independent of the study investigative team and will report progress including safety concerns to the project principal investigator. Safety concerns will be also be reported to the IRB.

- 1. Safety:** Safety will be monitored at intervals related to patient enrollment. Safety and device protocols will be reviewed by the medical monitor every twenty patients to assure uniform and safe application of project devices. Research staff will report skin irritation or bright light related symptoms as they occur via event evaluation forms. In addition, research staff will identify and immediately report unanticipated problems, unexpected adverse events and serious adverse events (defined below). Safety concerns will be also be reported to the IRB.
- 2. Protocol Compliance:** The project medical monitor will check enrolled patients for compliance with IRB requirements, conformance with informed consent procedures, verification of source documents and investigator compliance. One in ten patients will be randomly selected for conformance.
- 3. Event Evaluation:** Adverse event or unanticipated problem occurrence will prompt an event evaluation and a report to the project medical monitor. The adverse event report will NOT include identifying patient information but will otherwise provide a clinical summary of the study patient and the circumstances immediately associated with the adverse event / unanticipated problem including date of the event, type of event and a narrative event description.

Flow Diagram for Adverse Event / Unanticipated Problem Detection, Review and Reporting:

Unanticipated Problems are defined as any incident, experience, or outcome that meets all of the following criteria: 1) unexpected, 2) related or possibly related to participation in the research, and 3) suggests that the research places subjects or others at a greater risk of harm than was previously known or recognized.

Adverse Events: An **adverse event** will be defined as any untoward or unfavorable medical occurrence in a human subject, including any abnormal sign, symptom, or disease, temporally associated with the subject's participation in the research, whether or not considered related to the subject's participation in the research (modified from the definition of adverse events in the 1996 International Conference on Harmonization E-6 Guidelines for Good Clinical Practice). Adverse events that occur during study enrollment will be reported by research staff to the project medical monitor via an event evaluation.

A serious adverse event is any adverse event temporally associated with the subject's participation in research that meets any of the following criteria (modified from the definition of serious adverse drug experience in FDA regulations at 21 CFR 312.32(a)):

1. results in death or is life-threatening
2. requires prolongation of existing hospitalization
3. results in a persistent or significant disability/incapacity
4. results in a congenital anomaly/birth defect
5. any other adverse event that, based upon appropriate medical judgment, may jeopardize the subject's health and may require medical or surgical intervention to prevent one of the other outcomes listed in this definition

Response to Adverse Event: All study patients are (by definition) concurrently admitted to the MICU. The response to any adverse event will be appropriate medical care. Adverse event occurrence will prompt an event evaluation and report to the project medical monitor by research staff.

The project medical monitor will evaluate adverse events along the parameters of relationship, severity, and expectedness:

Relatedness:

1. Unrelated: Adverse event(s) clearly not related to the project
2. Unlikely: Adverse event(s) doubtfully related to the project
3. Possibly: Adverse events(s) may be related to the project; known to occur, but the temporal relationship is unclear; other causes are possible or biologically very plausible
4. Probably: Adverse event(s) likely associated with the project; known to occur and temporal relationship is appropriate; other causes are unlikely
5. Definitely: Adverse event(s) clearly associated with the project

Severity: The following scale will be used to grade the severity of adverse events noted during the study:

1. Mild adverse event: Did not interfere with normal activity, minimal symptoms, no intervention required
2. Moderate adverse event: Interfered with normal activity to some extent, moderate symptoms, minimal or local intervention required
3. Severe adverse event: Prolonged hospitalization with need for intervention to prevent escalation of condition
4. Life-threatening / disabling adverse event: Event that puts the patient at risk of death at the time of the event if immediate intervention is not undertaken
5. Fatal adverse event

Expectedness: An unexpected adverse event is any adverse event occurring in one or more subjects in a research protocol, the nature, severity, or frequency of which is not consistent with either (1) the known or foreseeable risk of adverse events associated with the procedures involved in the research that are described in (a) the protocol-related documents such as the IRB-approved research protocol and the current IRB-approved informed consent document, and (b) other relevant sources of information, such as product labeling and package inserts; or (2) the expected natural progression of any underlying disease, disorder, or condition of the subject(s) experiencing the adverse event and the subject's predisposing risk factor profile for the adverse event.

The **principal investigator ([name])** will have overall responsibility for adverse event reporting to Yale University's IRB and NHLBI. Unanticipated problems, unexpected adverse events or serious adverse events will be reviewed by the medical monitor. **The principal investigator will provide reporting of any of the following to the IRB and NHLBI within 5 days of occurrence:**

1. Unanticipated problems, unexpected adverse events or serious adverse events that are possibly, probably or definitely related to study protocols.
2. IRB approved revisions to the project which change participant risk.
3. Notice of any actions taken by the Yale University IRB regarding the project and any responses to these actions.

POTENTIAL BENEFITS

This research has the potential to benefit future patients admitted to the MICU via improved circadian entrainment. There is minimal risk involved in this study, and appropriate precautions to guard against risk have been taken. This protocol is intended for broad distribution following the research study. The findings of this research will be generalizable to a significant portion of MICU patients and thus provide potential future benefit to many critically ill patients, especially those at greatest risk for delirium (older age, history of hypertension).

RESEARCH ALTERNATIVES AND ECONOMIC CONSIDERATIONS

1. **Alternatives:** What other alternatives are available to the study subjects outside of the research? The alternative is to not participate and to receive usual care in the Medical ICU.

2. **Payments for Participation (Economic Considerations):**

Study subjects will receive a \$100 pre-paid gift card upon completion of study day 5 as compensation for their time and any minor inconveniences they may have experienced while participating in the study. In order to be eligible for study payment, subjects must complete through day 5 of the study protocol unless they are discharged from hospital prior to day 5. If a subject is discharged from the hospital prior to study day 5 but after study day 2, they will receive payment for their participation. In the event a study subject wishes to discontinue study participation before the end of study day 5 for any reason other than listed above, they will no longer be eligible for payment.

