- a. **Setting:** The study site is the medical intensive care unit (MICU) at Yale-New Haven Hospital (YNHH), York Street Campus and St. Raphael's Campus. Median ICU stay is 3 days. Predominant reasons for admission are sepsis and acute respiratory failure. MICU rooms are private. There is currently a unit-wide sleep promotion protocol which limits care activities from 00:00 to 04:00.
- b. **Design:** Aim 1 and 2, prospective cohort study; Aim 3 pilot randomized controlled trial (RCT). Aim 3 which is not dependent on Aims 1 and 2 will be conducted first.
- c. **Cohort:** We will enroll 100 subjects at risk for ICU delirium. In addition, we will enroll 16 subjects into the pilot randomize control trial.
- d. **Inclusion and exclusion criteria:** This study will focus on adults at an increased risk for ICU delirium. We have selected age ≥ 50 years as an inclusion criteria to study middle-aged to older adults who are at increasing risk for delirium while not overly restricting our sample. We will not restrict patients based on admission severity of illness (APACHE II) because we think this is a critically important confounder and would like to study the effect of the full spectrum of severity of illness on our outcomes. We will exclude patients at significant risk for pre-existing circadian abnormalities (e.g. shift work). We will also exclude patients with co-morbid disease or medication use that makes measurement of urinary aMT6s or actigraphy unreliable. Table 2 lists inclusion and exclusion criteria.

Table 2: Inclusion Criteria	Exclusion Criteria

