
1. Hospital admission less than 30 hours as of noon on day of enrollment2. Expected to stay in the MICU ≥ 24 hours after enrollment3. Expected to produce ≥ 250 mL urine / day4. Age ≥ 50 years5. Able to understand English.	
At significant risk for pre-existing circadian abnormalities:
 
– Severe chronic brain injury (Injury greater than 30 days ago resulting in the inability to live independently) OR Acute brain injury of any severity (Injury less than 30 days ago including acute intracranial bleed, traumatic brain injury, central nervous system infection, tumor, hepatic encephalopathy)– Documented circadian disorder (<1% population) or blind/disease of the optic nerve– Current history of substance abuse including alcohol (use in last 30 days)– Transferred from an outside hospital– Homeless 
Unable to participate in study activities:
 
– History of bipolar disease (Bright light therapy possibly unsafe in this population).– Paralyzed (due to injury, disease or medications)

- e. **Recruitment:** Patient recruitment will follow Yale University consent procedures, and we will obtain HIC approval before starting study activities. MICU admissions will be screened daily via the EMR. Eligible patients will be approached within 30 hours of hospital admission. Before consent, the patient will be assessed for delirium via the Confusion Assessment Method for the ICU (CAM-ICU). If not delirious and able to communicate, the patient can provide consent; otherwise, a legally authorized

representative (LAR) as delineated by Connecticut State Law can provide consent.

- a. In cases which the LAR provides consent, assent from the patient will be attempted daily and obtained whenever possible via simple verbal explanation of the purpose, activities, risks and benefits of the study.
- b. In the event a patient originally enrolled via LAR were to regain their capacity to consent themselves, trained study staff will follow the below protocol for re-consent.
 - i. Study staff will introduce identify themselves as a member of the research team and clarify that they are not part of the primary ICU team.

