 - ii. The protocol will be described to the patient; this description will include an overview of student events they already completed, cover in detail the study intervention and any remaining/future study procedures/events, and cover the risks associated with participation.
 - iii. We will assure study subjects that participation is voluntary and that the decision to continue their participation will have no impact on their current or future care.
 - iv. A copy of the consent document will be provided to the patient.
- f. **Timeline of Study Activities (Fig 2):** Patients will be enrolled within 30 hours of hospital admission and before 12:00 on the day of enrollment which is designated “Study Day 1 (D1).” Actigraphy, delirium monitoring, and light measurement (part of feasibility) will start no later than 12:00 on D1. Actigraphy and light measurement will continue until D5 or MICU discharge whichever is longer. If the patient is discharged from the hospital prior to day 5, all study activities stop upon hospital discharge. Study activities will continue if/when the patient is transferred to the general medical floor if the patient completes at least D2 (13:00) in the MICU. Delirium monitoring will occur until D30 or hospital discharge.

[figure not shown]

Figure 2: Study activities timeline.

APPROACH TO AIMS

Aim 1: Determine the association between ICU day-night light patterns and circadian abnormalities (i.e., circadian misalignment and decreased circadian amplitude).

Rationale: Aim 1 will test our hypothesis that non-circadian ICU light patterns are associated with increased circadian abnormalities as measured by urinary aMT6s. Our approach is to measure light levels (10-second intervals) and aMT6s (1-hour intervals, gold standard) for 72 hours following study enrollment; we will also collect exploratory measures of circadian rhythm, namely, actigraphy and heart rate. We will collect descriptive patient data to allow model adjustment during analysis. We define non-circadian ICU light patterns as abnormally low daytime light levels and abnormally high overnight light levels. We define circadian abnormalities as circadian misalignment and decreased circadian amplitude. The absence of circadian rhythm is an extreme decrease in amplitude (i.e., 100%). *This work will establish if non-circadian ICU light patterns are associated with the development of circadian abnormalities.*

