Research Design: We will enroll 100 subjects at increased risk for ICU delirium; subjects will be screened and consented as above. We will collect the following measures:

- a. **Room light levels** will be monitored from enrollment until Study D5 or until MICU discharge. We will set the light meter (HD450, Extech Instruments, New Hampshire) to read levels in lux at 10-second intervals. Meters will be placed in a standard location on the wall above the head of the bed as close as possible to eye level. Additional light measures will be taken adjacent to the patient's face (by holding the light meter next to their face for several seconds); these measures will be taken several times per day to assess light levels at or close to the eye.
- b. **Urinary aMT6s (1-hour intervals)** is the primary circadian measure for this aim. Melatonin is normally released just before habitual sleep time, and peak levels occur during sleep midpoint; urinary aMT6s peaks 2 hours after sleep midpoint.³⁸ For the proposed study, urinary aMT6s will be collected for 72 hours or until MICU discharge whichever occurs first. Urinary aMT6s will not be collected after MICU discharge. A 10mL aliquot of pooled urine sample collected every 1 hour will be used for analysis; total volume of urine will be recorded to allow for calculation of total aMT6s excreted. Total aMT6s excreted can be measured and is valid in patients with acute kidney injury, patients receiving diuretics,³⁹ and patients with decompensated cirrhosis.⁴⁰ We have the support of MICU nurse champions and the agreement of nursing leadership for the bedside nurse to collect these samples. Samples are stable at room temperature for 24 hours, will be transported to the lab daily, and stored at -80°C in the Translational Research Core. Samples will be batched and subsequently analyzed using a highly sensitive, competitive ELISA kit (IBL Laboratories, Germany).
- c. **Secondary measures** of actigraphy, surface body temperature, and continuous heart rate monitoring will be used in an exploratory manner. We plan to examine correlation with urinary aMT6s for use in future studies.

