Aim 1 Analytical Approach: Individual sleep midpoint will be calculated as halfway between habitual bedtime and habitual waketime as indicated during patient/surrogate interview questionnaire. Light dose will be calculated as the sum of mean lux per hour for each hour between 08:00 and 17:00 (day dose) and 22:00 and 06:00 (overnight dose). A day/night dose ratio will then be calculated by dividing the daytime light dose by the overnight light dose. Light dose ratio will be treated as continuous exposure variables, with higher numbers indicating a more favorable (circadian) exposure and lower numbers indicating a less favorable (non-circadian) exposure. Circadian alignment and amplitude will be calculated using time series analysis of urinary aMT6s using smoothing techniques to examine characteristics of circadian rhythm: acrophase (maxima) and nadir (minima). Statistical measures will evaluate for serial correlation, seasonality (periodicity), and trend. Longitudinal cosinor techniques will be used to test for alignment of nadir and acrophase with normal circadian phase and amplitude (e.g., individual sleep midpoint and estimated normal peak aMT6s).⁵⁵ The degree of misalignment versus normal will be recorded in minutes. The amplitude of the cycle will be defined as one-half of the difference between the acrophase and nadir and will be recorded in nanograms (ng) per hour.³⁰ Normal values have been identified for aMT6s.^{30,56} The assessment of circadian abnormalities for association with light patterns will be solely based on aMT6s analysis. Heart rate, iButton gradient readings, and actigraphy activity counts will be evaluated via cosinor techniques analogous to the aMT6s analysis described above. Actigraphy activity counts will also be evaluated by visual inspection of normalized mean activity per hour (Fig 3) and as described by Duclos et al.³² Confounder and effect modifier variables: Severity of illness will be calculated according to the APACHE II algorithm⁵⁷ and expressed as a continuous variable. Sepsis will be expressed as a categorical variable (absent, septic, septic shock) based on the sepsis-3 criteria.⁴⁷ The risk of OSA will be expressed as a categorical variable (low risk, high risk) based on the STOP-BANG algorithm.^{46,58} Overnight ICU care events per the timestamp data described above will be calculated as the number of ICU care events per hour between 22:00 and 06:00. Average daytime and overnight room temperature will be calculated as a continuous variable.

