
Testing for Associations: Because both measures of circadian abnormality (misalignment and decreased amplitude) are continuous and normally distributed, multivariable linear regression models will test for associations, with light dose ratio serving as the exposure. Linearity of the associations will be examined graphically, and higher order terms will be considered as necessary. Models will be adjusted for age, gender, severity of illness, sepsis, risk of OSA, ICU care events per hour, and room temperature variables. We will test for modification of the association between light dose ratio and the outcomes by sepsis and risk of OSA. Because of the non-trivial intra-correlation coefficient expected from the serial correlation of the repeated outcome measures over time, models will employ generalized estimating equations with an auto-regressive correlation structure. Model fit will be evaluated with residual analysis, and significance will be defined as a two-sided p-value ≤ 0.05 . Power Calculations. For both continuous, normally distributed outcomes, power calculations assume a two-sided alpha of 0.05, power of 90%, a sample size of 100, and prevalence of covariates ranging from 20% to 50%. For minutes of misalignment, we further assume a mean of 180 minutes with a standard deviation of 95 and for amplitude a mean of 450 ng with standard deviation of 180.³⁰ Under these assumptions, our sample of 100 is sufficient to detect a range of minimal average shifts between 52-65 minutes of misalignment, and 98-123 ng of urinary aMT6 per

incremental change in the explanatory variables.

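### Power for Aims 1 and 2 makes no allowance for short or missing aMT6s records, although urine collection ends at MICU discharge

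*Combined protocol and SAP*

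**What the plan says.** **Collection.** The Aim 1 Rationale describes measuring "aMT6s (1-hour intervals, gold standard) for 72 hours following study enrollment". Aim 1 Research Design, item b, sets the operative rule: "urinary aMT6s will be collected for 72 hours or until MICU discharge whichever occurs first". It adds: "Urinary aMT6s will not be collected after MICU discharge". Study Risks states that urine comes only from patients already catheterized and that nobody is catheterized for the study. Table 2 does not make a catheter an entry criterion.

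**Stay and entry.** Project Overview, item a, gives the unit's figure: "Median ICU stay is 3 days". Table 2 sets the entry window ("Hospital admission less than 30 hours as of noon on day of enrollment") and the stay criterion ("Expected to stay in the MICU ≥ 24 hours after enrollment").

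**Analysis.** Statistical Considerations, Aim 1, derives misalignment (minutes) and amplitude (ng per hour) from aMT6s by smoothing and longitudinal cosinor methods. It also says "Statistical measures will evaluate for serial correlation, seasonality (periodicity), and trend". Aim 1 uses GEE with an autoregressive structure for repeated outcomes. Aim 2 enters misalignment and amplitude as exposures in a Poisson model of delirium days.

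**Power.** Aim 1 assumes "power of 90%, a sample size of 100". Aim 2 uses 80, after removing 20% for delirium on the day of enrollment. No section gives a minimum record, an evaluable set, a replacement rule or an attrition allowance for aMT6s.

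**The concern.** Misalignment and amplitude are the Aim 1 outcomes and the Aim 2 exposures, and the plan rests the light analysis on aMT6s alone. How much aMT6s a patient supplies depends on MICU discharge or death and on whether a catheter is in place. The power statements nevertheless treat every counted patient as fully measured.

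Two things are at stake. First, the claimed 90% power is too high if any patient cannot be scored. Second, records of unequal length give phase and amplitude of unequal precision. In Aim 2 that error sits in the exposure. Classical error of this kind pulls the association with delirium days toward zero, and a Poisson model that takes each value as exact does not correct for it. Record length also plausibly follows severity of illness, so absent or short records may be informative.

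**Working it through.** **1. The plan's own figures.** The sample count reproduces: 100 × (1 − 0.20) = 80.

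The Aim 1 detectable shifts do not reproduce from the stated inputs. With shift = (1.960 + 1.2816) × SD / √(N·p·(1 − p)), N = 100 and p = 0.5 or 0.2:
- misalignment (SD 95): 3.2416 × 95/5 = 61.6 and 3.2416 × 95/4 = 77.0 min, against 52–65 stated
- amplitude (SD 180): 116.7 and 145.9 ng, against 98–123 stated

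For Aim 2, ln RR = 3.2416 × √(1.2 / (80 × 3 × Var(x))). With SD 95/60 = 1.583 and 180/100 = 1.8 units, this gives RR 1.156 and 1.136, against 1.12 and 1.08 stated.

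The gap is a separate matter. In Aim 1, an unstated covariate R² of about 0.29 would explain it, since 1 − (52/61.6)² = 0.29. Below I scale the stated figures, which needs only the ratio of sample sizes.

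**2. Record lengths (assumed, not documented).** Let S(t) be the chance of still being in the MICU t hours after MICU admission, with S(72) = 0.5, and let enrollment occur d hours after MICU admission.
- Under 72 h of urine = 1 − S(d + 72)/S(d)
- Under 24 h = 1 − S(d + 24)/S(d)
- Under 72 h, given that everyone stays 24 h = 1 − S(d + 72)/S(d + 24)

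| Assumed stay curve, d = 30 h | S(30) | S(54) | S(102) | <24 h | <72 h | <72 h if all stay 24 h |
|---|---|---|---|---|---|---|
| Weibull, shape 0.8 | 0.709 | 0.577 | 0.400 | 19% | 44% | 31% |
| Exponential | 0.749 | 0.595 | 0.375 | 21% | 50% | 37% |
| Log-normal, sigma 0.6 | 0.928 | 0.684 | 0.281 | 26% | 70% | 59% |

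Over the wider grid (log-normal sigma 0.6–1.2, Weibull shape 0.8 and 1.5, exponential; d from 0 to 30 h), the share under 72 h is 44–70% with no screening effect and 31–59% if all stay 24 h. The share under 24 h is 3–26% with no screening effect and 0% if the stay forecast is always right. Patients without a catheter are additional and cannot be sized from the documents.

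**3. Effect on power.** If a fraction f is unscorable, N′ = N(1 − f). Power = Φ(3.2416 × √(1 − f) − 1.960). Detectable shifts, and ln RR, are divided by √(1 − f).

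| f | N Aim 1 / Aim 2 | Power | Misalignment, min | Amplitude, ng | RR per 60 min | RR per 100 ng |
|---|---|---|---|---|---|---|
| 0 | 100 / 80 | 90% | 52–65 | 98–123 | 1.12 | 1.08 |
| 5% | 95 / 76 | 88.5% | 53–67 | 101–126 | 1.123 | 1.082 |
| 10% | 90 / 72 | 86.8% | 55–69 | 103–130 | 1.127 | 1.085 |
| 20% | 80 / 64 | 82.6% | 58–73 | 110–138 | 1.135 | 1.09 |

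Starting instead from the values recomputed in step 1, a 20% loss gives 68.9–86.1 min, 130.5–163.1 ng, RR 1.176 and RR 1.153.

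**4. Precision of a short record.** For whole cycles of n hourly values with independent noise, the standard error of peak time is about √(2/n) × (noise SD / amplitude) × 1440/(2π) minutes. Going from 72 to 24 h multiplies it by √3 = 1.73.

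As an illustration, take amplitude 450 (the plan's mean) and assume noise SD 200 with lag-one correlation 0.5. The correlation inflates the error by √(0.75 / (1.25 − cos 15°)) = 1.62. The result is 29.4 × 1.62 = about 48 min from 24 h and 28 min from 72 h. Simulation gives 47–49 and 27–28 min. With noise SD 400, simulation gives 105–110 and 56–57 min. The ratio is thus about 1.7 to 2. The noise values are assumptions.

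**The case against.** The strongest reply is that the variable window is deliberate and that no planned analysis requires 72 hours. A fixed 24-hour cosinor can be fitted to one cycle of hourly samples. That stands. A reader might infer that patients without 72 hours are lost, leaving about 50 and 40 patients and 63% power. The documents do not support this.

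A reader might also infer that at least half the cohort falls short of 72 hours. The 3-day median describes the whole unit from ICU admission. Later enrollment shortens the remaining stay, the stay criterion selects longer ones, and the net effect is unknown.

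Nor is it right that Aim 1 simply weights all patients equally. The plan specifies GEE and longitudinal cosinor methods, under which longer records may contribute more observations, although the repeated unit is not defined. This does not help Aim 2, which has one delirium count per patient and no correction for exposure error.

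The Timeline of Study Activities ties continued activities on the floor to completing the MICU stay to 13:00 on day 2, about 25 hours after noon on day 1. So early exits were foreseen. But this is a retention rule; it defines no analysis set and adds nothing to the power text.

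The planned adjustment for severity, and in Aim 2 for ventilator-free days and sedatives, may remove part of any bias from informative record length. The residual bias is not shown. Finally, comparing the simulated errors with the plan's SD of 95 min does not prove that SD too small, because it comes from an earlier study and may already contain measurement error.

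**Conclusion.** The point holds in a limited form. The collection rule, the catheter restriction and the merely expected stay make records of unequal length certain for practical purposes, and records under one cycle or absent possible. The power statements allow for none of this. The cost in power is moderate: at 5–20% unscorable, 90% becomes 88.5–82.6%, taking the plan's 90% as given. If stays are forecast perfectly and every patient has a catheter, the loss is nil.

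The shares under 72 h (roughly 30–70%) and under 24 h (0% to about 25%) rest on an assumed 72-hour median and assumed curve shapes. Unequal precision matters most in Aim 2, where it affects the exposure. Its direction under classical error is toward the null, but its size cannot be given because the documents do not state the hourly noise.

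**What to change.** 1. **Statistical Considerations, Aim 1 and Aim 2 power.** Replace 100 and 80 by an expected evaluable number, with the definition of a usable record and the assumed loss stated. Restate power and detectable effects on that number, as in the last table row if 20% is assumed.
2. **Statistical Considerations, Aim 1 and Aim 2 analysis.** Estimate phase and amplitude from one mixed-effects 24-hour cosinor fitted to all hourly values, so that short records contribute according to their precision. Carry that uncertainty into the Aim 2 Poisson model by a joint model or a measurement-error correction. Add a sensitivity analysis limited to patients with at least 24 hours of urine. As the main rule, that limit would select on discharge or death after enrollment. A separate complete-night condition is unnecessary: enrollment is before noon, so 24 continuous hours from then cover the night.
3. **Reporting.** Count patients without a usable record by reason (MICU discharge, death, no catheter) and compare them with scored patients.

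The cost is a somewhat more complex model and less favourable stated detectable effects, with no added patients or samples. Keeping 100 scored patients instead would mean enrolling 106, 112 or 125 at 5%, 10% or 20% loss (100/0.95, 100/0.90, 100/0.80, rounded up).
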